### 6.4. Appendix 4: Medical History

**Historical illnesses** are defined as the conditions/events with an **end date prior** to the informed consent date.

**Pre-existing conditions** are defined as the conditions/events with a **start date prior** to the informed consent date and with **an end date on or after** the informed consent date.

Following TFLs will be created

- Summary of Pre-existing Conditions
- Listing of Historical Illnesses
- Listing of Pre-existing Conditions and Adverse Events
- Listing of Pre-existing Conditions

## 6.5. Appendix 5: Treatment Compliance

“Treatment compliant to study intervention” is defined as “treatment compliance >= 75%” where,

$$\begin{aligned} \text{Treatment compliance (\%)} \\ = 100 \times \frac{\text{Number of injections administered}}{\text{Number of injections administered} + \text{not administered}} \end{aligned}$$

The numerator and denominator are based on CRF (Exposure: Dulaglutide).

Frequency counts and percentages of participants compliant to study intervention will be summarized by treatment arm using the ITT population. Its listing will be created.

Of the participants in the ITT population, frequency counts and percentages of participants prematurely discontinuing study interventions, including the reason for premature discontinuation, will be presented by treatment arm.

A Kaplan-Meier analysis of time from randomization to premature study intervention discontinuation by treatment arm will be provided.

## 6.6. Appendix 6: Prior and Concomitant Therapy

Medications will be classified into anatomical therapeutic chemical (ATC) drug classes using the latest version of the World Health Organization (WHO) drug dictionary. Medication start and stop dates will be compared to the date of first dose of treatment in each treatment period to allow medications to be classified as concomitant for each treatment period.

**Prior medications** are those medications that start prior to the date of first dose and stop prior to or on the date of first dose of study intervention.

**Concomitant medications** are those medications that start before, on, or after the first day of study intervention of the defined treatment period and continue into the treatment period.

Following Prior and/or Concomitant medication TFLs will be created:

- Summary of General Concomitant Medication
- Listing of General Concomitant Medication
- Listing of Prior/Concomitant Oral Antidiabetic Agents
- Summary of Oral Anti-Diabetic Medication (Prior Medications)
- Summary of Dose Modification of Oral Anti-Diabetic Medication **During the Study Period**
  - It is based on the baseline OAM. For example, if a patient with baseline OAM biguanide starts DPP-4 inhibitors after randomization, it will not appear in this table.
  - The modification is categorized as Decreased/Increased/Stopped.
  - Fisher Exact test is used for the treatment comparison (Decreased events).
- Summary of OAM Mean Daily Doses (mg/day)
- Listing of Insulin Therapy for Severe, Persistent Hyperglycemia (See Section 4.6.3.5.1)

- Summary of Insulin Therapy for Severe, Persistent Hyperglycemia During the Treatment Period (See Section 4.6.3.5.1)
  - Note: Fisher Exact test is used for the treatment comparison.

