In case of weekly DPP-4i, it must be stopped 1 week before randomization.

Visit 3

At Visit 3, participants should arrive at the study site in an at least 8-hour fasting state. In the fasted status, intake of water is allowed.

After confirming participant eligibility, participants will be randomized in a 2:1 ratio to weekly injections of dulaglutide 1.5 mg or 0.75 mg at Visit 3.

Randomization will be stratified by pre-study OAM class and HbA1c at Visit 1.

Stratification factors	Groups
pre-study OAM class	SU biguanides TZD a-GI glinides SGLT2i DPP-4i
HbA1c at Visit 1	low (<8.5% for DPP-4i class and <9.0% for other OAM classes) high ($\geq 8.5\%$ for DPP-4i class and $\geq 9.0\%$ for other OAM classes)

Abbreviations: a-GI = alpha-glucosidase inhibitors; DPP-4i = DPP-4 inhibitor; HbA1c = hemoglobin A1c; OAM = oral antihyperglycemic medications; SGLT2i = sodium-glucose, cotransporter type 2 inhibitors; SU = sulfonylureas; TZD = thiazolidinedione.

Participants will be instructed on how to use the Single-use pen and will inject their first dose of study intervention under the supervision of study personnel while in the clinic for Visit 3, after

randomization and other study procedures . The date and time of the first dosing of study intervention should be recorded on the eCRF.

Participants are required to continue using their concomitant OAMs, except for DPP-4i, throughout the treatment period. If a participant uses daily DPP-4i, it is required that the participants stop using daily DPP-4i at randomization.

Following randomization, participants will participate in a 52-week treatment period.

Treatment Period (Visit 3 to Visit 9)

Procedures during the treatment period will be performed as shown in the SoA (Section 1.3).

From Visit 3 through Visit 9 (except Visit 4), participants should arrive at the study site in an at least 8-hour fasting state. In the fasted state, intake of water is allowed.

Throughout the treatment period, participants will collect all of the following data in the participant diary:

- SMBG,
- dosing dates and time,
- hypoglycemic events,
- AEs, and
- concomitant medications.

The study site personnel will review the data at the next office visit.

At each office visit,

- study diaries will be collected,
- new study diaries will be dispensed (and instructions will be reviewed),
- used and unused study intervention and injection supplies will be returned, and
- new supplies will be dispensed as needed.

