At Week 52 or the early termination (ET) visit, all used and unused study intervention will be returned.

Discontinuation or dose changes of concomitant OAMs are not permitted, except in certain situations (Section 6.5). Participants will be permitted to use concomitant medications that they require during the study, except certain medications that may interfere with the assessment of efficacy and safety characteristics of the study intervention (Section 6.5).

Safety Follow-Up Period

Procedures during the safety follow-up period will be performed as shown in the SoA (Section 1.3).

All participants who complete the treatment period (both I and II) are required to complete Visit 801, a safety follow-up visit approximately 4 weeks after the last visit of the treatment period. During the safety follow-up period, participants will not receive study intervention.

The safety follow-up period will also be applied to participants who discontinue from the study. In this case, the Safety Follow-Up visit (Visit 801) will occur approximately 4 weeks after the ET visit.

Participants are required to return any remaining study diaries to the study site at the end of this period.

Early Termination Visit

Every attempt will be made to keep participants in the study irrespective of their adherence to treatment with study intervention.

At any time after Visit 3 (randomization), a participant who is to discontinue from the study before Visit 9 will have an ET visit conducted. At this visit, procedures will occur as shown in the SoA (Section 1.3). Participants should be instructed to return any remaining used or unused study intervention supplies and diaries to the study site at this visit. Participants will be asked to perform the Safety Follow-Up visit (Visit 801) approximately 4 weeks after the ET visit, so that the Safety Follow-Up visit (Visit 801) will be their final visit. If the participant is not able to perform the Safety Follow-Up visit (Visit 801), the ET visit will be the final study visit. A participant summary electronic case report form (eCRF) will be completed.

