9.4.2.3. Concomitant Therapy

Concomitant medications, including previous therapy for diabetes, will be summarized by anatomical therapeutic chemical classification and treatment arm using the ITT population. In particular, the incidence of rescue therapy for severe, persistent hyperglycemia will be analyzed as an exploratory safety endpoint. Dose modifications of oral antihyperglycemic medications will also be compared between treatment arms.

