#### 4.7.1.3. OAM Subgroup Analyses

All Table/Figure analysis (e.g., demographic, treatment compliance, efficacy, safety) will be conducted for the following OAM subgroups unless otherwise specified.

- DPP-4 inhibitors (DPP-4i)  
Note: This is a monotherapy of dulaglutide.
- Sulfonylureas (SU)
- Biguanides (BG)
- Alpha-glucosidase inhibitors (a-GI)
- Thiazolidinedione (TZD)
- Glinides
- Sodium-glucose cotransporter type 2 inhibitors (SGLT-2i)
- Combination therapy (SU, BG, a-GI, TZD, Glinides, or SGLT-2i)

When statistical models are used (e.g., MMRM, ANCOVA, logistic regression) “pre-study OAM class” model term will be excluded.

For example, for SU subgroup, MMRM model of **Analysis of HbA1c (%)** will include following terms:

- treatment, baseline value, visit, the interaction of treatment-by-visit

The statistical models do not include the OAM subgroup-treatment interaction as a model term. Therefore, no interaction will be tested (using p-value).

The subgroup analysis specified in Section [4.7.1.1](#) or Section [4.7.1.2](#) (e.g. Age, Sex) will not be conducted for the OAM subgroups.

If OAM subgroup results are redundant, they will not be created, for example, “Summary of Dose Modification of Oral Anti-Diabetic Medication” and “Summary of OAM Mean Daily Doses (mg/day)”.

For Kaplan-Meier analysis, odds ratio and p-value will not be produced if estimates are unavailable due to small events or sample size, or figure may not be created.

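### The only planned test of changes to background oral antihyperglycemic medication (OAM) counts dose decreases and leaves out OAMs that were stopped

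*SAP*

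**What the plan says.** Protocol 9.4.2.3 (Concomitant Therapy) commits to a comparison: "Dose modifications of oral antihyperglycemic medications will also be compared between treatment arms". It sets no limit on the kind of modification.

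Protocol 4.1 puts stopping and dose change together under one restriction: "Discontinuation or dose changes of concomitant OAMs are not permitted, except in certain situations (Section 6.5"). Section 6.5 gives hypoglycemia as the occasion on which an OAM dose may be modified.

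SAP 6.6 plans a summary of OAM dose modification during the study period. On its basis it says "It is based on the baseline OAM". On its rows it says "The modification is categorized as Decreased/Increased/Stopped". On its test it says "Fisher Exact test is used for the treatment comparison (Decreased events"). No test is stated for the stopped or increased rows, or for the summary of OAM mean daily doses listed next to it. SAP 4.9, on changes to protocol-planned analyses, reads NA.

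For the DPP-4 inhibitor class, Protocol 4.1 says "it is required that the participants stop using daily DPP-4i at randomization". A weekly DPP-4 inhibitor is stopped one week before randomization. SAP 6.6 does not say whether these participants are in the table.

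**The concern.** A complete withdrawal of the background OAM is the largest cut-back possible, yet in this test it has the same status as no change at all. The protocol names discontinuation beside dose change, so the SAP's test is narrower than the comparison the protocol announces, and no reason is given.

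Two things depend on the comparison. It is part of the evidence on what the higher dose costs in combination use. It also shows whether background therapy stayed equal between arms. That second use matters because the intercurrent events in SAP 1.1.1 are rescue medication and discontinuation of study treatment. An OAM reduction or stop is neither, so HbA1c values after one stay in the efficacy analysis.

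A second gap is the table population. If the DPP-4 inhibitor class were counted and pooled with the others, its stops by design would fill the stopped row.

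**Working it through.** **The plan's own figures.** Neither document gives an expected rate of OAM changes, so there is no stated figure for this table to reproduce. The stated design figure does reproduce: 352 and 176 evaluable participants, a difference of 0.3 and an SD of 1.0 give power 0.901 by the normal approximation and 0.900 by the noncentral t, against the stated 90% or more. The strata add up (Protocol 9.2): 150 + 75 = 225 on DPP-4 inhibitors, 240 + 120 = 360 on other OAMs, and 225 + 360 = 585.

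**Inputs.** Denominators are 240 (1.5 mg) and 120 (0.75 mg), the planned participants on a continuing OAM. All event counts below are assumptions. Stops are taken to be participants without an earlier decrease, so the two counts add. The test is the two-sided Fisher exact test.

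**Step 1: effect of leaving out stops.**

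| Assumed decreases | Decreased only | Assumed stops | Decreased or stopped |
|---|---|---|---|
| 12 vs 2 | 5.00% vs 1.67%, p = 0.155 | 12 vs 2 | 24 vs 4: 10.00% vs 3.33%, p = 0.035 |
| 12 vs 3 | 5.00% vs 2.50%, p = 0.40 | 6 vs 1 | 18 vs 4: 7.50% vs 3.33%, p = 0.16 |
| 12 vs 3 | same | 3 vs 3 | 15 vs 6: 6.25% vs 5.00%, p = 0.81 |
| 12 vs 3 | same | 6 vs 6 | 18 vs 9: 7.50% vs 7.50%, p = 1.0 |
| 12 vs 3 | same | 1 vs 5 | 13 vs 8: 5.42% vs 6.67%, p = 0.64 |

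For the 12 vs 3 rows, the difference of 2.50 points becomes 4.17, 1.25, 0 and -1.25. Omitting stops hides a difference in some cases and creates or reverses one in others.

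**Step 2: effect of the denominator, if DPP-4 inhibitor participants were counted.** Percentages for decreases are multiplied by 360/585 = 0.615. The test hardly moves:
- 12 vs 2: p = 0.155 on 240/120 and 0.158 on 390/195
- 24 vs 4: p = 0.035 and 0.038
- 12 vs 3: p = 0.402 and 0.406

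The movement in Step 1 therefore comes from the omitted stops, not from the denominator.

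**Step 3: effect on the stopped row, if DPP-4 inhibitor stops were counted and pooled.** By design 150/390 = 38.5% and 75/195 = 38.5% would be in that row. Assumed real stops of 6 vs 1 would read (150 + 6)/390 = 40.0% vs (75 + 1)/195 = 39.0%, p = 0.86. On 240/120 the same stops read 2.5% vs 0.8%, p = 0.43. Neither is significant, but the pooled row hides the pattern.

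**Step 4: do the documents put DPP-4 inhibitors in the table?** For inclusion: the table rests on the baseline OAM and no class is excluded. Against: SAP 6.6 classes as prior medication those drugs that "stop prior to or on the date of first dose of study intervention". The first injection is given at the randomization visit, so a DPP-4 inhibitor stopped on schedule is a prior medication, and prior OAMs have their own summary. SAP 4.7.1.3 also says "If OAM subgroup results are redundant, they will not be created", and gives this table as an example. That suggests it is already broken down by OAM, in which case DPP-4 inhibitor stops would have their own row. The text does not settle the matter.

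**The case against.** The strongest reply is that little depends on this table. It is a concomitant-therapy summary, not a primary or secondary endpoint. Hypoglycemia is analysed directly, by incidence and rate and by level. Stops stay visible as a category by arm, and OAM mean daily doses and an OAM listing are also planned. Layout and denominators may be set in the separate table specifications that SAP Section 1 mentions. All of this stands, and it keeps the point minor. It does not explain why the one stated test omits a category that the table already holds.

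A second reply is that a stop is not a clean marker of hypoglycemia: an OAM may be stopped for other reasons, for example in a therapy switch after study drug is discontinued. This also stands. It is a reason to keep the decreased-only result and to limit the counting window, not to leave stops untested.

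A reader might infer two stronger points. One is that the comparison is biased toward no difference. That would need stops to split between arms as decreases do, and nothing in the documents says so; Step 1 shows shrinkage and reversal just as easily. The other is that the stopped row is uninformative because 225 of 585 participants fall in it by design. That requires DPP-4 inhibitor stops to be counted and pooled. The SAP does not state this, and its prior-medication definition and redundancy note point the other way. Nor do the documents say that an OAM dose cannot go below the Appendix 7 minimum maintenance dose, which is an entry criterion.

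**Conclusion.** The point holds in a limited form. It is certain from the text that the only stated between-arm test of OAM changes omits stops, that this is narrower than the protocol's comparison, and that no reason is recorded. The tested number of cut-backs is incomplete whenever a participant's OAM is stopped without an earlier recorded decrease. How far, and in which direction, the arm difference is affected depends on how stops split by arm. The p-values shown rest on assumed counts and only illustrate the range.

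The unstated table population is a gap to close, not a demonstrated error. Its effect on the decreased-only test is negligible, and its effect on the stopped row arises only if DPP-4 inhibitor stops are pooled. The primary analysis and the sample size are not touched.

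**What to change.** In SAP 6.6:

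1. State the table population: participants on a continuing OAM (planned 240 and 120), with pre-study DPP-4 inhibitor participants excluded or shown separately.
2. Apply the Fisher test at participant level to decreased or stopped combined, counting each participant once and only changes up to permanent discontinuation of study drug.
3. Keep the decreased-only result beside it, because stops can have causes other than hypoglycemia, and keep the three categories as descriptive rows.

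If the sponsor prefers to test decreases only, SAP 4.9 should say so and give the reason.

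The cost is a few lines of SAP text and one table specification. The categories are already planned, so no new data are needed.

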## 6.7. Appendix 7: Protocol Deviations

Protocol deviations will be identified throughout the study. Important protocol deviations are defined as those deviations from the protocol likely to have a significant impact on the completeness, accuracy, and/or reliability of the study data or that may significantly affect a participant's rights, safety, or well-being.

Refer to a separate document called "GBGQ Trial Issues Management Plan" for the important protocol deviations with categorizations.

The number and percentage of participants having IPD(s) will be summarized within

- ❖ Protocol Deviation Category,
- ❖ Study Specific Deviation Term

by treatment group.

A by-participant listing of important protocol deviations will be provided.

## 6.8. Appendix 8: Impact of COVID-19

Impact of pandemic (e.g., COVID-19) on analyses will be collected Disposition CRF (for disposition). Protocol deviation/mitigation will be collected through Clinical Trial Management System (CTMS). Those are identified as having the text "COVID-19:" at the beginning of their descriptions.

Impact of pandemic (e.g., COVID-19) on analyses will be systemically addressed.

Following TFLs will be created:

- Listing of Patient Disposition Affected by COVID-19
- Summary of Protocol Deviations/Mitigation Related to COVID-19
  - Note: It include following categories:
    - ❖ Protocol Deviation Category,
    - ❖ Study Specific Deviation Term.
- Listing of Protocol Deviations/Mitigation Related to COVID-19

## 6.9. Appendix 9: Annual Report Analyses

Based on regulatory requirements for the Development Safety Update Report (DSUR), reports will be produced (if not already available from the study CSR) for the reporting period covered by the DSUR.

## 6.10. Appendix 10: Clinical Trial Registry Analyses

Additional analyses will be performed (if not already available from the study CSR) for the purpose of fulfilling the Clinical Trial Registry (CTR) requirements.

Analyses provided for the CTR requirements include the following:

Summary of AEs, provided as a dataset, will be converted to an XML file. Both serious adverse events (SAEs) and 'Other' AEs are summarized by treatment group and by MedDRA PT.

- An AE is considered 'Serious' whether or not it is a TEAE.
- An AE is considered in the 'Other' category if it is both a TEAE and is not serious. For each SAE and 'Other' AE, for each term and treatment group, the following are provided:
  - the number of participants at risk of an event,
  - the number of participants who experienced each event term, and
  - the number of events experienced.
- Consistent with [www.ClinicalTrials.gov](http://www.ClinicalTrials.gov) requirements, 'Other' AEs that occur in fewer than 5% of participants in every treatment group may not be included if a 5% threshold is chosen (5% is the minimum threshold).
- AE reporting is consistent with other document disclosures for example, the CSR, manuscripts, and so forth.

## 6.11. Appendix 11: Unblinding Plan

Unblinding details are specified in a separated unblinding/blinding plan.

